### **2.3. Intervention**

An established TYOH 2.0 core team of two coaches and four youth lived expert advisors will collaborate with [name] and the TYOH 2.5 research team on modifying the leadership guide currently being used in the TYOH 2.0 study (Appendix B: Leadership Guide) so it can be delivered as an in-person, four-week (two sessions/week) leadership program. They will be joined by a high school teacher (and former ECPP teacher at Covenant House Toronto) who will help align the guide with the Ontario Ministry of Education core high school learning competencies for potential consideration of high school credits for leadership program completion (note: we will unlikely be able to guarantee a high school credit at this pilot stage, but plan to develop the guide with this goal in mind for our planned scale-up).

At the same time the leadership guide is being modified, the team will collaborate on how best to deliver material during the four-week, in-person program (Table 1). The leadership sessions will be held in a public library, last approximately three hours, and be led by coaches from our current study with our youth advisors participating as paid leadership interns. Participants will be paid \$25.00/hour for attending the program and receive a certificate upon program completion.

**Table 1. TYOH 2.5 Leadership Program\***

SESSION	KEY FOCUS/ACTIVITES
1 (Week One)	

• Consent forms

• Baseline questionnaires

• Examine link between mindfulness and purpose

2 (Week One)	

• Explore core values

• Create a vision board

3 (Week Two)	

• Examine link between core values and mood

• Create a daily routine

4 (Week Two)	

• Discover strategies to develop good habits

• Understand difference between excellence and perfection

ONE WEEK BREAK	
5 (Week Three)	

• Review pre-break key learnings

• Explore link between identity and behaviour

• Develop strategies to live in alignment with positive identity

6 (Week Three)	

• Examine growth mindset vs. fixed mindset

• Explore link between purpose and connecting with others

7 (Week Four)	

• Explore concept of scarcity

• Understand link between vulnerability, courage, and worthiness

8 (Week Four)	

• Review and share key learnings

• Discuss next steps

• Complete questionnaires

• Celebration meal

• Focus group

*Note: A more comprehensive/detailed session-by-session agenda will be developed in collaboration with youth advisors during the co-design stage.	

## 2.4. Study Outcomes

The primary outcomes for this pilot program are feasibility and acceptability (Table 2).

Secondary outcomes include knowledge of program material and identity capital (Table 2).

Exploratory outcomes are differences in primary/secondary outcomes by sub-groups (e.g., gender, age, identification as 2SLGBTQ+, child welfare involvement) and/or program participation levels (Table 2).

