**Table 2. TYOH 2.5 Key Outcome Variables and Instruments**

Key Outcome Variables	Instruments	Collection Timepoints*
Primary Outcomes		
Feasibility and Acceptability	Recruitment and enrollment metrics Session attendance Dropout metrics Focus group Composite program feedback questionnaire	T0 T1/T2 T1/T2 T2 T2
Secondary Outcomes		
Knowledge of Program Material	Composite knowledge assessment scale	T1/T2
Identity Capital	Multi-Measure Agentic Personal Scale (MAPS20; Côté, 2016)	T1/T2
Exploratory Outcomes		
Subgroup Differences	Baseline Demographic Questionnaire Session attendance Focus group	T1 T1/T2 T2
*Pre-program = T0; Week One = T1; Week Four = T2		

The decision to incorporate the leadership program into an adequately powered definitive trial (alongside rent subsidies and coaching) will be based on feasibility and acceptability. We will not incorporate the leadership program into our planned national larger study if we find program attendance is less than 50%, more than 30% of participants drop out, and/or qualitative feedback from program participants is overwhelmingly negative.

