## **2.8. Data Collection**

To answer *Objective Three* (intervention feasibility and acceptability), we will utilize quantitative measures consisting of recruitment/enrolment/attendance/dropout metrics (see Appendix H: Attendance Log) and a composite program feedback questionnaire along with qualitative measures consisting of focus groups (Tables 2 & 5). To answer *Objective Four* (assessing whether self-reported measures of identity capital and knowledge of program material show improvement immediately post-program compared to baseline), we will utilize MAPS20 (assessment of identity capital; Côté, 2016) and a composite knowledge assessment scale (Tables 2 & 5). To answer *Objective Five* (exploring whether there are differences in outcomes by sub-group and/or program participation levels), we will examine select variables from the baseline demographic questionnaire and attendance/dropout metrics (Tables 2 & 5). Given the differences in time commitment at each data collection session, youth will be paid a data collection honorarium of \$25 at pre-program data collection and \$50 at post-program data collection (Appendix I: Study Budget and Justification).

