**Table 5. Quantitative Instruments**

Instrument	Psychometric Properties
Baseline Demographic Questionnaire	This 18-item self-report measure was developed for this study and explores domains related to: age; gender; race/ethnicity; sexual orientation; immigration status; child welfare involvement; homelessness entrenchment; education; social support; financial support; food security.
MAPS20 (Côté, 2016)	This 20-item validated self-report measure explores domains related to identity capital: self-esteem; purpose in life; internal locus of control; self-efficacy/ego strength. Score range: 20-120; score of less than 71 indicates risk/vulnerability of being overwhelmed by any adverse circumstances (internal consistency of four sub-scales $\alpha = .61-.75$ ).
Knowledge Assessment	This 16-item self-report measure was developed for this study and explores domains related to self-leadership such as: mindfulness; core values; purpose; goal setting; growth mindset; identity; courage.
Composite Program Feedback Questionnaire	This 4-item anonymous questionnaire will be used to collect information about participants' view of the leadership program, the impact of the program on them, and their view of the individuals running the program.

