### **2.8.2. Quantitative Analysis**

Quantitative analysis will be conducted using descriptive statistics to measure feasibility and acceptability overall (Objective 3) and by select sub-groups (Objective 5). Non-parametric or t-tests and Cohen's d effect size will be used to examine pre/post leadership program differences in identity capital (MAPS20) and acquired knowledge (Objective 4), and by select sub-groups and program attendance (Objective 5). Biostatistician [name] (co-investigator) will provide oversight to the quantitative data analysis.

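### Section 2.4 compares attendance and dropout by attendance, and the planned attendance comparisons of MAPS20 and knowledge are self-selected and unadjusted

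*Combined protocol and SAP*

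**What the plan says.** Section 2.4 defines the exploratory outcomes: "Exploratory outcomes are differences in primary/secondary outcomes by sub-groups (e.g., gender, age, identification as 2SLGBTQ+, child welfare involvement) and/or program participation levels". Table 2 lists these instruments for the primary outcomes of feasibility and acceptability: "Recruitment and enrollment metrics Session attendance Dropout metrics Focus group Composite program feedback questionnaire". For the exploratory comparison it lists: "Baseline Demographic Questionnaire Session attendance Focus group". Session attendance is therefore both a primary outcome and the variable that defines participation level. Section 2.8 says of Objective 5 that "we will examine select variables from the baseline demographic questionnaire and attendance/dropout metrics".

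Section 2.8.2 is narrower. It describes feasibility and acceptability overall and by sub-group, without mentioning attendance. Attendance enters only in the next sentence, where t-tests or non-parametric tests and Cohen's d are applied to MAPS20 and knowledge pre/post differences "and by select sub-groups and program attendance (Objective 5"). No adjustment is stated, and no section defines a participation level.

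The limitations in section 3 cover low power, the urban Ontario setting, self-report and the adequacy of the measures. Self-selection by attendance is not among them.

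**The concern.** There are two separate problems.

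The first is one of definition. If attendance or dropout is the outcome and attendance is the grouping variable, a difference is guaranteed and carries no information.

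The second is one of inference. Attendance is decided after baseline, by the youth. Motivation, housing stability and similar factors can affect both how often a young person comes and how much their scores change. An unadjusted comparison of frequent and infrequent attenders mixes any program effect with these differences, and there is no control group to separate them. The pilot is meant to generate data and hypotheses for a national scale-up, so an attendance gradient reported without a caveat could be carried forward as a dose-response.

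**Working it through.** **Which primary components are circular.** The five primary instruments in Table 2, set against participation level:

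| Component | Compared by attendance |
|---|---|
| Recruitment and enrolment metrics | Precede participation; not applicable |
| Session attendance | Circular |
| Dropout metrics | Circular |
| Focus group | Not circular, but held at the end of session 8, so only those present contribute |
| Feedback questionnaire | Anonymous (Table 5); as described, cannot be linked to a youth's attendance |

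Circularity covers two of five.

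**Size of the self-selection effect.** The plan states no alpha, power or effect size, so it has no figure to reproduce. The check is a simulation with a true program effect of zero.

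- From the documents: 15 + 15 = 30 enrolled; 8 sessions; T1 at session 1 and T2 at session 8.
- Assumed: each youth has an attendance propensity u ~ N(0,1). All attend session 1. Each later session is attended with probability 1/(1 + exp(−(1.2 + u))). T2 scores exist only for those at session 8 (about 22 youth on average). Change score = r·u + √(1 − r²)·e, with e ~ N(0,1). The correlation r is varied because the documents give no value.
- Analysis: mean difference between 7–8 sessions and fewer, and linear regression of change on sessions attended, two-sided 0.05, 4000 runs per setting.

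| r | Apparent difference (SD) | p < 0.05 in regression |
|---|---|---|
| 0 | 0.0 | 5% |
| 0.3 | 0.31 | 13% |
| 0.5 | 0.53 | 29% |
| 0.7 | 0.75 | 56% |

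The difference is close to proportional to r: 0.31/0.3, 0.53/0.5 and 0.75/0.7 are all between 1.03 and 1.07. The two groups thus differ by roughly one SD in propensity, and r carries that over to the change score.

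A second model used the two-group t-test (at least 7 of 8 sessions versus fewer), seven equal knowledge domains, an attendance logit of 1.4 + u and about 23 youth with T2 data. It gave 0.31, 0.51 and 0.75 SD, with p < 0.05 in 10%, 18% and 33% of 3000 runs. The apparent difference agrees between models; the rejection rate depends on the test.

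**Within-youth contrast for knowledge.** Some domains in Table 5 ("mindfulness; core values; purpose; goal setting; growth mindset; identity; courage") resemble session topics in Table 1, such as "Explore link between identity and behaviour" in session 5. If items can be tied to sessions, a youth's gain on items from attended sessions can be compared with their gain on items from missed sessions, with youth and session effects. Assuming two items per session, sessions 2–7, r = 0.5 and 2000 runs:

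| Setting | Mean estimate | p < 0.05 |
|---|---|---|
| No effect, absence unrelated to topic | 0.00 | 6.8% |
| No effect, moderate topic-related absence | 0.14 | 15% |
| No effect, strong topic-related absence | 0.26 | 38% |
| True effect 0.5 per session | 0.50 | 89% |
| True effect 0.5, review gives absentees half | 0.25 | 39% |

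Estimates are in item-change units, with overall SD about 0.8 to 0.9. In the topic-related rows, interest in a topic raises the log-odds of attending by 0.5 or 1.0 per SD and the gain by 0.3 per SD. About 15 of the 22 or so completers contribute. The contrast removes stable differences between youth. It does not remove topic-related absence, and the review content in sessions 5 and 8 dilutes it.

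**The case against.** The strongest reply is that the operative text is 2.8.2, which already keeps attendance away from the primary outcomes. On this view the circularity lies in one summary sentence with an 'and/or'. That largely stands: 2.4 needs aligning, and no planned primary analysis needs replacing. A reader might infer that all primary outcomes by participation level are circular; the component table above shows that only attendance and dropout are.

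Next, the analysis is labelled exploratory and section 3 already asks for caution. That limits the weight of the point but does not answer it. The stated caution concerns power, which is about missed effects, whereas self-selection produces apparent effects that are not there.

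A reader might infer that the gradient would drive the scale-up. The rule after Table 2 uses attendance below 50%, dropout above 30% and overwhelmingly negative qualitative feedback, so this comparison cannot change it. Nor do the documents say that a gradient would be read as a program effect.

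It is also tempting to present the within-youth contrast as an unbiased replacement. The documents do not support that. The Table 1 agenda is provisional by its own footnote, the Table 5 domain list is illustrative, no item-to-session key is given, and MAPS20 cannot be tied to sessions. Nor can goal setting be treated as untaught because no session bears that name: the vision board, daily routine and habits content in sessions 2 to 4 may well teach it.

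**Conclusion.** The point holds in limited form. Section 2.4 is circular for two of five primary components and is out of step with 2.8.2. For MAPS20 and knowledge, the planned comparison can show an attendance gradient of about 0.3 to 0.75 SD with no program effect, if attendance propensity and gain correlate at 0.3 to 0.7. That correlation is an assumption; at zero the spurious difference vanishes. The result also rests on the assumed attendance model and on T2 data coming only from session 8 attenders. This is a cheap improvement to an exploratory analysis and does not touch the go/no-go rule.

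**What to change.** 1. In 2.4, limit participation-level comparisons to knowledge and MAPS20, matching 2.8.2.
2. In 2.8.2, take participation level as the number of sessions attended. For each measure, regress the post-program score (or the change) on sessions attended and the baseline score; with baseline in the model the sessions coefficient is the same either way. Report the estimate with 95% CI and the number with T2 data, and label it a non-causal association.
3. In section 3, add self-selection by attendance as a limitation.
4. Optionally, if the final agenda supports an item-to-session key fixed before recruitment, add the within-youth knowledge contrast with youth and item effects. Present it as a supplement and not a replacement, describe it as less confounded and not unbiased, state both weaknesses (topic-related absence, dilution by the reviews), and do not use goal setting as an untaught control.

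Items 1 to 3 need no new data, since baseline scores and an attendance log are already planned. The cost is a few sentences and a little extra analysis. The optional item also needs the key and item-level, session-level records. Baseline adjustment can remove only the part of self-selection reflected in the baseline score, so the caveat stays necessary.

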**Table 2. TYOH 2.5 Key Outcome Variables and Instruments**

Key Outcome Variables	Instruments	Collection Timepoints*
Primary Outcomes		
Feasibility and Acceptability	Recruitment and enrollment metrics Session attendance Dropout metrics Focus group Composite program feedback questionnaire	T0 T1/T2 T1/T2 T2 T2
Secondary Outcomes		
Knowledge of Program Material	Composite knowledge assessment scale	T1/T2
Identity Capital	Multi-Measure Agentic Personal Scale (MAPS20; Côté, 2016)	T1/T2
Exploratory Outcomes		
Subgroup Differences	Baseline Demographic Questionnaire Session attendance Focus group	T1 T1/T2 T2
*Pre-program = T0; Week One = T1; Week Four = T2		

The decision to incorporate the leadership program into an adequately powered definitive trial (alongside rent subsidies and coaching) will be based on feasibility and acceptability. We will not incorporate the leadership program into our planned national larger study if we find program attendance is less than 50%, more than 30% of participants drop out, and/or qualitative feedback from program participants is overwhelmingly negative.

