**Table 4. Eligibility Screening**

	Yes	No
16 – 24 years of age (at baseline)		
Have experienced homelessness (e.g., unstable housing arrangements including shelter stays, couch surfing, and foster care) for 3 consecutive months in the past 12 months		
Able to provide free and informed consent		
Able to speak and read English well enough to give consent and participate in the intervention and data collection		
Left homelessness within the past 12 months		
Be able to participate in the four-week, in-person leadership program (attend at least 6/8 sessions)		
NOT enrolled in a program or study with similar features to TYOH 2.5		
MUST SAY “YES” TO ALL TO BE ELIGIBLE FOR ENROLLMENT		

After eligibility screening, participants will be informed immediately over the phone whether they are eligible or ineligible for the study. If there is any confusion regarding eligibility and/or capacity to consent, the team member will reach out to [name] for guidance. In addition to being the study principal investigator, [name] is a nurse practitioner with over a decade of experience working exclusively with young people who are experiencing or have experienced homelessness.

Eligible participants will be provided the date/time/location of the first leadership program session. At the beginning of the first session, a research team member will carefully review the consent form with the participants to ensure they have a solid understanding of the study, with particular attention to: 1) overall study aim; 2) study length; 3) data collection; 4) data security; and 5) dissemination. A concerted effort has been made to ensure the consent form is in plain language. Highlighted throughout the document is the fact that informed consent is an ongoing process and can be negotiated at any time.

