### **2.8.1. Quantitative Methods**

Quantitative data collection (Appendix J: Quantitative Data Collection Instruments) will be conducted at the beginning of the first leadership program session as well as the last (Tables 3 &

5). T1 (Week One) data collection will consist of: baseline demographic questionnaire; MAPS20 (Côté, 2016); and knowledge assessment. T2 (Week Four) data collection will consist of: MAPS20; knowledge assessment; and program feedback questionnaire. All questionnaires will be completed in-person and on paper.

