## **2.9. Data Monitoring**

As is common in pilot and feasibility studies, there is no interim quantitative analysis planned to guide a decision to stop the study early (Eldridge et al., 2016). That said, at least one member of our research team will attend every leadership session to monitor participant engagement. We will consider making adjustments to the leadership program if informal feedback from participants is overwhelmingly negative and/or the majority of young people stop participating.

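### Does the lack of a written definition of dropout and of program attendance leave the two numerical no-go limits in section 2.4 unusable?

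*Combined protocol and SAP*

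**What the plan says.** Section 2.4 makes feasibility and acceptability the primary outcomes. After Table 2 it sets two numerical limits, "program attendance is less than 50%, more than 30% of participants drop out", and adds a third, qualitative ground for not proceeding. Any one of the three is enough.

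Table 2 lists session attendance and dropout metrics on separate lines, both collected at T1/T2, with recruitment and enrollment metrics at T0. Its footnote reads "Pre-program = T0; Week One = T1; Week Four = T2". Consent is taken at Session 1 (section 2.7): "At the beginning of the first session, a research team member will carefully review the consent form with the participants". The limits therefore apply most naturally to youth who consent.

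Section 2.8 names the data source as "recruitment/enrolment/attendance/dropout metrics (see Appendix H: Attendance Log". Section 2.8.2 says feasibility is described overall and by sub-group.

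Other places touch on participation without linking it to the 30% limit:

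- Table 4 screens on "Be able to participate in the four-week, in-person leadership program (attend at least 6/8 sessions".
- Section 2.3 says youth "receive a certificate upon program completion".
- Section 2.8.1 says quantitative data collection "will be conducted at the beginning of the first leadership program session as well as the last".
- Section 2.9 would consider adjusting the program if "the majority of young people stop participating".
- Section 4.1 notes the right to withdraw.

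**The concern.** These are the only numerical limits on the primary outcome, and they feed the decision about a national study. The protocol text does not say what makes a participant a dropout. Candidates include formal withdrawal, ceasing to attend, absence from the last session (when the post-program data are collected) and attending fewer than 6 of 8 sessions. These need not coincide. Nor does the text say whether attendance is averaged over everyone who consented or only over those still coming.

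A research team member attends every session, so the pattern is known as it develops. If the definition were chosen afterwards, the same pilot could be placed on either side of a limit.

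**Working it through.** **Inputs from the protocol.** 15 + 15 = 30 youth (section 2.6), taken here as the number who consent. 2 × 4 = 8 sessions (section 2.5, Table 1), so 30 × 8 = 240 person-sessions. The limits are 50% and 30%. The protocol gives no expected attendance or dropout rate, so every rate below is an assumption.

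**What the limits mean in counts.** The dropout limit is crossed at 10 or more of 30 (9/30 = 30.0% does not exceed 30%). The attendance limit is crossed at 119 or fewer of 240 (120/240 = 50.0% is not below 50%).

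**Attendance.** With all consenters in the denominator and 8 sessions each, the pooled rate, the mean over participants and the mean over sessions are the same number. Averaging is therefore not an ambiguity. Two others can be constructed:

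- *Dropping leavers from the denominator.* Suppose 9 of 30 leave after Session 2 and the other 21 average 4 sessions. Attendance is 4/8 = 50.0% among those remaining, and (9×2 + 21×4)/240 = 102/240 = 42.5% among all. The two readings split only while the 21 average from 4.0 to just under (120 − 18)/21 = 4.86 sessions. That needs dropout to sit exactly on its own limit while youth screened as able to attend 6 sessions average fewer than 5. Nothing in the protocol suggests removing leavers.
- *Share reaching 6 of 8 instead of a mean.* If 14 youth attend 8 sessions and 16 attend 4, the mean is (14×8 + 16×4)/240 = 176/240 = 73.3%, while the share is 14/30 = 46.7%. This reading borrows a screening criterion that the protocol does not attach to the limit.

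**Dropout, one illustrative log.** 3 youth stop after Session 2, 8 attend 5 of 8, 19 attend 7 of 8, and 7 of the 27 still coming miss Session 8. Mean attendance is (3×2 + 8×5 + 19×7)/240 = 179/240 = 74.6%.

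- Stopped: 3/30 = 10.0%
- Absent from Session 8: (3 + 7)/30 = 33.3%
- Fewer than 6 of 8: (3 + 8)/30 = 36.7%

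Only the two readings that count absence as dropout cross 30%.

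**Dropout, a simple model.** Everyone attends Session 1. A share w stops after Session 2. The rest attend each later session independently with probability p. The dropout probability q per youth is:

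- stopped: w
- no Week Four session: w + (1 − w)(1 − p)²
- absent from Session 8: w + (1 − w)(1 − p)
- fewer than 6 of 8: w + (1 − w)·P(Bin(7, p) ≤ 4)

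The chance of crossing the limit is P(Bin(30, q) ≥ 10). Mean attendance is w·2/8 + (1 − w)(1 + 7p)/8.

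| w, p | Mean attendance | Stopped | No Week Four session | Absent from Session 8 | Fewer than 6 of 8 |
|---|---|---|---|---|---|
| 0, 0.80 | 82.5% | 0% | 0.0% | 6.1% | 0.9% |
| 0, 0.70 | 73.8% | 0% | 0.02% | 41% | 65% |
| 0.10, 0.75 | 72.8% | 0.05% | 1.28% | 53% | 50% |
| 0.10, 0.80 | 76.8% | 0.05% | 0.48% | 32% | 14% |

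In simulation, the last three definitions fail to agree in 75% of pilots (w = 0, p = 0.70), 68% (0.10, 0.75) and 37% (0.10, 0.80). In the first of these nobody stops at all, so every crossing is occasional absence given another name.

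Now compare the two readings based on stopping. Every youth who stops also has no Week Four session, so the disagreement is the difference between the two columns: 0.02% − 0 = 0.02%; 1.28% − 0.05% = 1.23%; 0.48% − 0.05% = 0.43%.

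**The case for a change.** The strongest reply is that readings close to ordinary usage can still split. Take a log in which 16 youth attend all 8 sessions, 8 stop after Session 4 (4 of them withdraw formally), 4 stop after Session 6 and 2 miss only Session 8. Mean attendance is 198/240 = 82.5%. Formal withdrawal gives 4/30 = 13.3%, never returning after the break 8/30 = 26.7%, absence from both Week Four sessions 12/30 = 40.0%, and absence from Session 8 14/30 = 46.7%. The protocol chose numbers for these limits and left judgement to the qualitative ground, so a numerical limit deserves a rule. Being a pilot is no excuse either, since the decision to proceed is the main output.

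Part of this stands. The available text does not define dropout, and formal withdrawal can differ from ceasing to attend. But formal withdrawal alone is a strained reading when section 2.8 refers to an attendance log for the dropout metrics and section 2.9 speaks of youth who stop participating. That log form was not available, so a definition there cannot be ruled out.

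A further example sets 8/28 = 28.6% among consenters against 10/30 = 33.3% of all who accepted a place. It does not help, because no-shows belong to the T0 recruitment and enrollment metrics, which carry no limit.

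**Conclusion.** The concern identifies missing detail, not an error. Attendance has a natural formula that can be computed from the log. Dropout has an ordinary meaning, withdrawing or no longer coming, that fits the separate listing in Table 2 and the attendance-log source. Under the assumed model, two readings of that kind put the pilot on different sides of 30% in about 0.02% to 1.2% of cases. The much larger figures depend on counting occasional absence as dropout.

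No stated rule is shown to give a wrong answer, the limits themselves are not in question, and more than one single definition would serve. For a 30-person pilot with descriptive feasibility analysis, the team can fill the gap sensibly.

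This rests on 30 consenters, independent attendance across sessions and assumed rates, since the protocol gives none. Later or more gradual stopping, as in the log above, would widen the difference between stopping-based readings.
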